6 STUDY PROCEDURES

See next page for Schedule of Evaluations (6.1)

PFD (Pelvic Floor Disorder) Questionnaires consist of 3 validated short-form (in English and Spanish) PFD questionnaires (already used as standard of care at patient intake): Pelvic Floor Distress Inventory (**PFDI-20**⁷³), Pelvic Floor Impact Questionnaire (**PFIQ-7**⁷³), Pelvic Organ Prolapse/ Urinary Incontinence Sexual Function Questionnaire (**PISQ-IR**⁷⁴) *plus* a 6-question survey of **vaginal atrophy symptomatology**⁷⁵, a general quality-of-life (QoL) instrument (**SF-12**), and a **body image questionnaire**.

Schedule of Evaluations (Table 1)Assessment	Baseline (≥5wk before Surgery)	Preop Visit (w/in 2wk of surgery)	Surgery/ Hospitalization	1mo Postop Visit (±2wk)**	3mo Postop Call (±2wk)	6mo Postop Visit (5-7mo)	9mo Postop Call (±2wk)	12mo Postop Visit (10-14mo)	18&30mo Postop Calls (±2wk)	24&36mo Postop Visits (±2mo)
Informed Consent Form, Inclusion/Exclusion, Randomization	X									
Demographics	X									
Medical History	X									
Exam: POP-Q	X			X		X		X		X
Exam: Levator muscle strength assessment	X	X		X		X		X		X
Exam: Vaginal atrophy assessment	X	X	X	X		X		X		X
Exam: vaginal epithelium/ granulation tissue assessment	X	X		X		X		X		X
Medication Review	X	X		X	X	X	X	X	X	X
PFD Questionnaires	X	X			X*	X	X*	X	X*	X
PGI-I and/or PGI-S	X					X		X		X
Vaginal Maturation Index	X		X					X		
Blood Serum (E1, E2)	X							X		
Blood (whole), storage for DNA/ genetics assessment (optional)	X									
Vaginal Wall Biopsy (optional)			X							
Study Cream ^{Tube No.} delivery/receipt	X ¹		X ²		X ³	X ⁴	X ⁵			
Medication Calendar ^{Tube No.} collection		X ¹			X ²	X ³	X ⁴	X ⁵		
Preop History/Exam		X								
Postop Med/Surg update				X	X*	X	X*	X	X*	X
Postop Extra Treatment				PRN	PRN	PRN	PRN	PRN	PRN	PRN

Adverse Event, Protocol Deviation forms	PRN	PRN	PRN	PRN	PRN	PRN	PRN	PRN	PRN	PRN
---	-----	-----	-----	-----	-----	-----	-----	-----	-----	-----

POP-Q, pelvic organ prolapse quantification examination; PFD, Pelvic Floor Disorder; PGI-I and –S, Patient Global Impression of Improvement, - Severity; E1, estrone; E2, estradiol

*, At these times (3, 9, 18 and 30-mo postoperatively), these are phone call “visits” only with no questionnaires or exam. However, the coordinator will phone the participant to query and document: (a) if she has symptoms of a bulge or, “something falling out that you can see or feel in your vaginal area”, which is Question #3 of the PFDI-20; (b) she has had treatment for pelvic organ prolapse since the last visit date; (c) she is experiencing new medical problems or complications; (d) she has been hospitalized, had surgery, been to the emergency department, or visited a doctor for urologic or gynecologic conditions since the last visit date; and (e) she has had any change in her medications. A reminder of the next in-person study visit is also given.

**, Clarification of timing of postoperative visits: the 1-month postop visit is defined as one calendar month after surgery. For example, if surgery is on July 1, one month postop is Aug 1, then ± 2 week. This is to differentiate from surgery date + *4 weeks* or surgery date + *30 days*. Likewise, the 6-month postop visit is January 1, ± 1 month; and the 12-month postop is July 1 of the following year, ± 2 months.

6.2 Description of Evaluations

6.2.1 Consent/Screening Evaluation

Consenting Procedure

At the same patient encounter, both the consenting process and patient screening will occur. Generally, this will be the patient's initial encounter in the Urogynecology clinic but it may be at any visit at which the patient selects surgical repair of symptomatic pelvic organ prolapse; for example, perhaps she previously had been managed with conservative measures such as pessary placement. The informed consent and the history and exam findings will be collected in a private room. The informed consent document will be written and provided in English or Spanish. Translator services are available at all study sites. Either the research coordinator or another member of the research team (PI or co-investigator) will be obtaining the consent, and the patient will sign and date/time her name to indicate understanding, which will be observed and countersigned by a witness.

Annual review of the consent document will be done in conjunction with continuing review by each clinical site's Institutional Review Board (IRB), and updates will be made as deemed appropriate. If other modifications to the document are deemed necessary by the research team (e.g., a change in protocol or known risk of study intervention), these modifications will be communicated to the IRB for approval.

Screening

Screening for eligibility will be relatively simple. Most inclusion/exclusion criteria are readily assessed from the patient's *routine intake history and physical examination* completed as part of usual care upon presentation to a Urogynecology clinic. For example, this history/exam would have already identified a symptomatic postmenopausal patient with prolapse not using any form of estrogen supplementation and an exam consistent with the eligibility criteria: stage 2 or greater anterior and/or apical prolapse and BMI ≤ 35 kg/m². No unique laboratory, radiology, or other invasive examination or testing is required to determine study eligibility beyond the history and examination performed as part of routine care in a Urogynecology clinic.

There is no set maximum allowable time between which study eligibility may be determined and beginning study participation. The visit at which randomization occurs and study drug is dispensed (Tube #1) is deemed the Baseline visit, and eligibility should be re-confirmed at this time.

6.2.2 Enrollment, Baseline, and/or Randomization

Enrollment

In this study, a single informed consent will encompass both screening and study procedures (as screening procedures are a part of routine care). Enrollment and randomization will occur on the same day all screening criteria are met and the individual agrees to participate. This enrollment/randomization date will be captured on a case report form at the *Baseline assessment*.

Baseline Assessments

- Contact Information (**Form 01**): name, address, phone, email data from patient and an alternative contact. Confirm patient's assent to being contacted by text and/or email.
- Demographics (**Form 02**): racial/ethnicity data and type of health insurance payer
- Medical History (**Form 03**): smoking history, confirmation of postmenopausal status, hysterectomy status, and assessment for history of recurrent urinary tract infection, diabetes, connective tissue disease, and various medical conditions
- Baseline Physical Exam (**Form 04**): gather height, weight, Pelvic Organ Prolapse Quantification (POP-Q) exam, uterine size, levator muscle tone and strength, investigator assessment of vaginal atrophy, and vaginal maturation index (VMI) specimen collection (see below).
- Medication Review (**Form 05**): list all medications related to treatment of incontinence and overactive bladder
- Pelvic Floor Disorder (PFD) Questionnaires (**Form 10**): *see description above in 6.1*
- Patient Global Impression of Severity (PGI-S) (**Form 11**): 1-question tool validated for urinary incontinence and modified for POP. Assesses overall impression of symptom severity related to POP.
- Vaginal Maturation Index (VMI): See also Section 5.4. A standard plastic spatula (similar to those used for a Pap smear and readily available in any gynecology clinic) will be used to sample the upper vaginal walls for 15-30 seconds. The spatula will be swirled in a ThinPrep® container (labeled with a preprinted barcode label with a Specimen ID linked with the participant's Subject ID number), which is then stable when stored at room temperature or 4°C and shipped with cold packs in a cold shipping box for storage at UTSW.
- Blood serum collection: Blood will be drawn into a standard red top tube. 5mL (1 teaspoon) is gathered to assess baseline estrone (E1) and estradiol (E2) levels.
 - Tube: Red top glass, no additive, no clot activator with uncoated interior, vacutainer tubes (BD366430 - 16 x 100 mm x 10.0 ml)
 - Do not draw from an IV or shunt.
 - Post-collection: allow to clot for 20-50min (room temperature)
 - Centrifuge (after balancing) at 1000-2000 g (RCF) for 15 minutes. Although most clinical blood centrifuges only spin at one speed, one will need to compute the rpm's of the specific centrifuge to give 1000-2000 g. The method to convert RCF in g's to rpms is based on the centrifuge's radius of rotation.
 - Using a transfer pipette, the serum is removed from the red top tube (being careful not to disturb the clot) and dispensed into a screw-on top plastic tube for transport.
 - The transport tube is capped securely. A preprinted barcode label with the Specimen ID is affixed.
 - The stopper is replaced in the original red top tube, which is discarded with the transfer pipette in a biohazard container.
 - Serum may either be shipped within 24 hr of collection on cold packs in

a cold shipping box or stored at -20°C and shipped on dry ice to UTSW (e.g., if bundling with other samples for efficiency).

- Whole blood collection (optional): Blood will be drawn into a standard yellow top tube. 5mL (1 teaspoon) is gathered at baseline. After appropriate processing and shipment, these specimens will be aliquoted and stored at UT Southwestern for possible future aims to include DNA analysis and studies examining for genetic predictors of surgical success/failure.

Randomization (Form 06)

Randomization to either active CE cream or placebo cream will be assigned by the research pharmacist using the allocation tables provided to him/her previously by the DCC. Stratification will be by site, hysterectomy status, and years since menopause (<10 and ≥10). The pharmacist is alerted to the subject once she has completed the consent process and has been assigned a Subject ID number. The 4-digit Randomization Number will be given by the pharmacist to the Research Coordinator. At this time, study drug may either be dispensed directly to the patient (via the Research Coordinator) or, if timing is preferable, may be shipped to the patient via FedEx. The patient is to begin study cream application immediately (that evening) once obtaining the cream and document use on the Medication Calendar.

- Dispensation of study drug (Tube #1) is documented (**Form 07**)
- Protocol Deviation (**Form 21**): as needed

6.2.3 Follow-up Visits

Preoperative Visit (within 2wk of Surgery):

- Medication Review (**Form 05**): *updated from Baseline*
- Medication Calendar documentation (**Form 07**) of study drug use Baseline-to-Pre-op
- Pelvic Floor Disorder (PFD) Questionnaires (**Form 10**)
- Preop Visit and Physical Exam (**Form 12**): assesses for any possible complaints or complications related to study cream application and re-assesses levator muscle tone and strength, and investigator assessment of vaginal atrophy Vaginal Maturation Index (VMI) for “Surgery” time point *may* be collected at this visit if it falls within 7 days of surgery.
- Adverse Events (**Form 09**) and Protocol Deviation (**Form 21**): as needed

Surgery/Hospitalization:

- Surgeon’s Report (**Form 13**): confirmation of VMI collection, investigator assessment of atrophy, surgeon assessment of tissue quality, confirmation of prolapse repair per protocol or reasons for deviation from protocol (if any), intraoperative complications.
- Hospitalization (**Form 14**): days hospitalized, bladder voiding status at discharge, immediate postoperative complications
- Return of study drug (Tube #1) and dispensation of Tube #2 is documented (**Form 07**). Tube #2 is dispensed to the subject with instructions to resume twice-weekly use once discharged home. The weight of Tube #1 is documented

and the tube appropriately disposed/destroyed.

- Medication Calendar (**Form 07**) documenting use of Tube #1 (Baseline-to-Surgery) is collected (if not already completed at Pre-op).
- Vaginal wall biopsy: an optional small full-thickness biopsy (triangle approximately 1.5x1 cm) will be obtained from the apical/ cephalad anterior vaginal wall (shown in figure below from an abdominal perspective). This is tissue that ordinarily would be discarded in the course of an anterior vaginal wall repair (colporrhaphy) procedure. This will be placed in buffered solution (RNAlater®). A preprinted barcode label with a Specimen ID is affixed. This is stable when stored at 4°C. It is shipped to UTSW on cold packs for later histologic assessment and qPCR for mRNA testing. Tissue collected locally at UTSW will initially be delivered for processing to the lab in phosphate-buffered saline (PBS), allowing additional analysis by zymography (protease enzyme activity), immunoblotting, and hydroxyproline assay for cross-linked collagen content.

[figure not shown]

Figure 4. Vaginal wall biopsy (For orientation, a suture is placed loosely on the mid-portion of the apical margin of the triangular specimen)

- Adverse Events (**Form 09**) and Protocol Deviation (**Form 21**): as needed

1-month Postoperative Visit (2-6wk Postop):

- Medication Review (**Form 05**): *updated from Preop Visit*
- Surgical pathology review is confirmed (**Form 14b**) and, if abnormal, prompts completion of adverse event documentation (**Form 09**)
- Postop Medical/Surgical History update (**Form 15**): documents any interval treatments for prolapse or urinary symptoms, interval medical history.
- Postop Exam (**Form 16**): re-assesses levator muscle tone and strength, investigator assessment of vaginal atrophy, examination for vaginal suture or mesh exposure/ ulcerations/ granulation tissue, and repeat POP-Q examination
- Postop Extra Treatments (**Form 17**): as needed
- Adverse Events (**Form 09**) and Protocol Deviation (**Form 21**): as needed

3-month Postoperative Phone Call (±2wk):

- Postop phone call documentation (**Form 18**) completed, with follow-up questions about feelings of vaginal pressure/ bulging and if there has been treatment for prolapse since the last study visit.
- Study cream Tube #3 is dispensed to the subject via FedEx with instructions to continue twice-weekly application.
- Medication Calendar (**Form 07**) documenting use of Tube #2 (Surgery-to-3mo) is collected either by mail or fax (or reminder to bring calendar to 6mo Postop Visit). Reminder to bring Study cream Tubes #2 and #3 to next appointment.
- Medication Review (**Form 05**): *updated from 1-month Postop Visit*
- Postop Extra Treatments (**Form 17**): as needed
- Adverse Events (**Form 09**) and Protocol Deviation (**Form 21**): as needed

6-month Postoperative Visit (± 1 mo):

- Study cream Tube #3 is collected (and #2, if not previously collected). Study cream Tube #4 is dispensed to the subject with instructions to continue twice-weekly application (**Form 07**). The weight of Tubes #2 and #3 are documented and the tubes appropriately disposed/destroyed.
- Medication Calendar documenting use of Tube #3 (3mo-to-6mo) is collected (**Form 07**).
- Medication Review (**Form 05**): *updated from 3-month Postop Call*
- Adverse Events (**Form 09**) and Protocol Deviation (**Form 21**): as needed
- Pelvic Floor Disorder (PFD) Questionnaires (**Form 10**)
- Patient Global Impression of Severity (PGI-S) and Patient Global Impression of Improvement (PGI-I) (**Form 11**): 1-question tools assessing overall impression of symptom severity and improvement related to POP.
- Postop Medical/Surgical History update (**Form 15**)
- Postop Exam (**Form 16**)
- Postop Extra Treatments (**Form 17**): as needed

9-month Postoperative Phone Call (± 2 wk):

- Postop phone call documentation (**Form 18**) completed, with follow-up questions about feelings of vaginal pressure/ bulging and if there has been treatment for prolapse since the last study visit.
- Study cream Tube #5 is dispensed to the subject via FedEx with instructions to continue twice-weekly application.
- Medication Calendar (**Form 07**) documenting use of Tube #4 (6mo-to-9mo) is collected either by mail or fax (or reminder to bring calendar to 12mo Postop Visit). Reminder to bring Study cream Tubes #4 and #5 to next appointment.
- Medication Review (**Form 05**): *updated from 6-month Postop Visit*
- Postop Extra Treatments (**Form 17**): as needed
- Adverse Events (**Form 09**) and Protocol Deviation (**Form 21**): as needed

12-month Postoperative Visit (± 2 mo):

- Study cream Tube #5 is collected (and #4, if not previously collected) (**Form 07**). The weight of Tubes #4 and #5 are documented and the tubes

appropriately disposed/destroyed.

- Medication Calendar documenting use of Tube #5 (9mo-to-12mo) is collected (**Form 07**).
- Medication Review (**Form 05**): *updated from 9-month Postop Call*
- Adverse Events (**Form 09**) and Protocol Deviation (**Form 21**): as needed
- Pelvic Floor Disorder (PFD) Questionnaires (**Form 10**)
- Patient Global Impression of Severity (PGI-S) and Patient Global Impression of Improvement (PGI-I) (**Form 11**)
- Postop Medical/Surgical History update (**Form 15**)
- Postop Exam (**Form 16**)
- Postop Extra Treatments (**Form 17**): as needed
- Specimen collection, preparation, and shipment to UTSW: blood/serum (sent on cold packs within 24 hr of collection *or* store at -20°C and ship on dry ice) and VMI (store at 4°C and ship on cold packs)

18-month Postoperative Phone Call (±2wk):

- Postop phone call documentation (**Form 18**) completed, with follow-up questions about feelings of vaginal pressure/ bulging and if there has been treatment for prolapse since the last study visit.
- Medication Review (**Form 05**): *updated from 12-month Postop Visit*
- Postop Extra Treatments (**Form 17**): as needed
- Adverse Events (**Form 09**) and Protocol Deviation (**Form 21**): as needed

24-month Postoperative Visit (±2mo):

- Medication Review (**Form 05**): *updated from prior call or visit*
- Adverse Events (**Form 09**) and Protocol Deviation (**Form 21**): as needed
- Pelvic Floor Disorder (PFD) Questionnaires (**Form 10**)
- Patient Global Impression of Severity (PGI-S) and Patient Global Impression of Improvement (PGI-I) (**Form 11**)
- Postop Medical/Surgical History update (**Form 15**)
- Postop Exam (**Form 16**)
- Postop Extra Treatments (**Form 17**): as needed

30-month Postoperative Phone Call (±2wk):

- Postop phone call documentation (**Form 18**) completed, with follow-up questions about feelings of vaginal pressure/ bulging and if there has been treatment for prolapse since the last study visit.
- Medication Review (**Form 05**): *updated from 12-month Postop Visit*
- Postop Extra Treatments (**Form 17**): as needed
- Adverse Events (**Form 09**) and Protocol Deviation (**Form 21**): as needed

36-month (Final) Postoperative Visit (±2mo):

- Medication Review (**Form 05**): *updated from prior call or visit*
- Adverse Events (**Form 09**) and Protocol Deviation (**Form 21**): as needed
- Pelvic Floor Disorder (PFD) Questionnaires (**Form 10**)

- Patient Global Impression of Severity (PGI-S) and Patient Global Impression of Improvement (PGI-I) (**Form 11**)
- Postop Medical/Surgical History update (**Form 15**)
- Postop Exam (**Form 16**)
- Postop Extra Treatments (**Form 17**): as needed

6.2.4 Completion/Final Evaluation

See 36-month Postoperative Visit above.

At the completion of 36 months or at the participant’s final visit (if early withdrawal), “Final Status” documentation (**Form 20**) will be completed. This gives the following possible reasons for withdrawal: ineligible/ screen failure (few, if any, of these are anticipated); subject never began Study Cream; subject did not complete/undergo surgery; subject voluntarily withdrew from study (reason specified); investigator withdrew patient from study (reason specified); lost to follow-up; death; transition to long-term resident or skilled nursing facility; study termination; other (reason specified).

Possible reasons for early withdrawal by the subject may include intolerance of the study medication, patient preference, or inability to continue with follow-up examinations and assessments. Early withdrawal of the participant by the investigator may also be for participant’s inability to adhere to study medication or visits.

If a participant withdraws (or is withdrawn) after randomization but before 12 months postoperatively, there is a prompt to the research coordinator/ physician examiner to collect a final VMI specimen.

It is not anticipated that participants will need to continue to be monitored after study withdrawal and discontinuation of the study medication.

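### Section 6.2.4 lets an investigator withdraw a woman for not adhering to the cream and foresees no monitoring afterwards, which is in tension with Section 8 and the as-randomised analysis

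*Combined protocol and SAP*

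**What the plan says.** Section 6.2.4 (Completion/Final Evaluation) lists reasons for leaving the study, to be recorded on Form 20. One is "investigator withdrew patient from study (reason specified". The text adds: "Early withdrawal of the participant by the investigator may also be for participant’s inability to adhere to study medication or visits". It sets no adherence threshold, and the wording permits withdrawal without requiring it. The section ends: "It is not anticipated that participants will need to continue to be monitored after study withdrawal and discontinuation of the study medication".

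For the final evaluation, 6.2.4 opens with "See 36-month Postoperative Visit above". For a woman who leaves after randomisation but before 12 months it says that "there is a prompt to the research coordinator/ physician examiner to collect a final VMI specimen".

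Section 8 (Intervention Discontinuation) says that women who stop the cream are still followed, with their permission, and that the schedule and length of follow-up do not change. A woman who withdraws voluntarily is asked to keep her scheduled evaluations, complete an end-of-study evaluation and give a VMI specimen. Section 8 does not mention withdrawal by the investigator. Section 7 continues monitoring after the cream is stopped for side effects, unless the woman has withdrawn from the study.

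Sections 5.4 and 9.5 define the primary analysis set as women randomised, operated on and assessed at least once after surgery, analysed by assigned group. Adherence is used only to define per-protocol subsets.

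**The concern.** Stopping the cream and leaving the study are different events. An as-randomised comparison needs outcomes from women who do the first without the second. Section 8 respects this. Section 6.2.4 opens a route by which the first can become the second on an investigator's decision, and Section 8 does not close it. Two sites could handle the same non-adherent woman differently and both be within the protocol.

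A woman withdrawn before her first postoperative assessment drops out of the modified intention-to-treat set. One withdrawn later stays in the set but has no 12-month outcome. If the cream works and women off it lose the benefit, the primary estimate then moves from the as-randomised effect toward the effect in adherers. Unlike ordinary dropout, this loss would come from the protocol's own wording, and the missing outcomes might not be recoverable at analysis.

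**Working it through.** **Which rule governs whom**

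| Situation | Section 6.2.4 | Section 8 |
|---|---|---|
| Stops cream, stays in study | Not addressed | Followed, schedule unchanged |
| Withdraws voluntarily | No need for monitoring foreseen | Asked to continue evaluations and complete an end-of-study evaluation |
| Withdrawn by investigator for non-adherence | Permitted; no need for monitoring foreseen | Silent |

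The last row is the gap.

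**Early final visit.** The visit that 6.2.4 points to, "36-month (Final) Postoperative Visit", lists Forms 10, 11, 15 and 16. Form 10 holds the bulge question and Form 11 the PGI-I. Form 15 "documents any interval treatments for prolapse or urinary symptoms". Form 16 is the postoperative examination, described at the 1-month visit as including levator, atrophy and epithelium checks "and repeat POP-Q examination". Every primary-outcome component is therefore covered if that list applies at an early exit. The text does not say so explicitly, and for investigator withdrawal Section 8 adds nothing.

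**Size.** The plan gives no figure for this loss. The inputs are:

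- 1-year success 65% control and 80% treated (Section 9.2). These imply a hazard ratio of ln(0.80)/ln(0.65) = 0.518; the plan states 0.5188.
- p, the share of the estrogen arm that is non-adherent. The documents offer three proxies: 9.8% (Section 2.2b, one-year discontinuation in another trial), 25% (Section 9.2, loss and non-adherence pooled) and 4/13 (Section 2.2a, the pilot, preoperative use only).
- f, the share of those women whom investigators withdraw. No document gives it, so it is varied.

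The assumptions are that non-adherent estrogen-arm women succeed at the control rate of 0.65, hazards are constant, prognosis is otherwise equal, withdrawal occurs at t = 0.5 year, and withdrawn women are censored then. Any placebo-arm withdrawals leave the control rate unchanged.

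As-randomised difference = 0.15 × (1 − p).

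With withdrawal, S(1) = A × B / C, and the difference is S(1) − 0.65, where

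- A = (1 − p)·0.80^t + p·0.65^t
- B = (1 − p)·0.80 + p(1 − f)·0.65
- C = (1 − p)·0.80^t + p(1 − f)·0.65^t

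Example, p = 0.25 and f = 0.25: A = 0.75 × 0.8944 + 0.25 × 0.8062 = 0.8724. B = 0.6000 + 0.1219 = 0.7219. C = 0.6708 + 0.1512 = 0.8220. S(1) = 0.8724 × 0.7219 / 0.8220 = 0.7661. The difference is 11.61 points against 11.25 as randomised, a shift of 0.36.

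Differences in percentage points, with the shift in brackets (computed before rounding):

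| p | As randomised | f = 25% | f = 50% | f = 100% |
|---|---|---|---|---|
| 9.8% | 13.53 | 13.69 (0.16) | 13.86 (0.33) | 14.23 (0.70) |
| 25% | 11.25 | 11.61 (0.36) | 12.02 (0.77) | 13.03 (1.78) |
| 4/13 | 10.38 | 10.81 (0.42) | 11.30 (0.91) | 12.57 (2.19) |

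For scale, the standard error of the difference with 94 per arm is √[(0.35 × 0.65 + 0.20 × 0.80)/94] = 0.064, or 6.4 points.

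If non-adherers keep half the benefit (success 0.725), the shift at p = f = 25% falls from 0.36 to 0.18 points. If the drug has no effect, and removal and prognosis are equal in both arms, the shift is zero.

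**The case against.** The best defence is that the documents already separate stopping the cream from leaving the study. Sections 7 and 8 both draw that line. The closing sentence of 6.2.4 applies only when withdrawal and discontinuation have both happened, and it can be read as being about safety monitoring. The withdrawal clause is permissive, investigators are blinded, and the likely shift is small against sampling error. All of that stands and limits the weight of the point. It does not say what happens to outcome data once an investigator has withdrawn a woman for non-adherence.

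Four stronger readings are tempting, and the documents do not support them.

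- A reader might infer that only a VMI specimen is collected at early exit. Section 8 separately asks voluntary withdrawers for an end-of-study evaluation, and 6.2.4 points to the 36-month forms. The gap is mainly for investigator withdrawal.
- A reader might take censoring of later withdrawals as the plan's rule. Section 9.5 names log-rank and Cox methods, and discusses imputation or mixed models for missing follow-up points, but does not say how such a woman enters the primary comparison. Censoring is a presumption.
- A reader might remove all non-adherers from the analysis set and obtain a much larger bias. That requires withdrawal before the first postoperative assessment, scheduled at 1 month. The 9.8% is a one-year figure and the 25% is pooled, so neither describes that window.
- A reader might use the 3.5% and 2.1% in Section 7.2 as removal rates. They are adverse events leading to drug discontinuation in another study, and Section 8 would keep such women in follow-up.

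**Conclusion.** The concern holds as a tension in the text. Section 6.2.4 permits withdrawal from the study for non-adherence with no monitoring foreseen afterwards. Section 8 and the modified intention-to-treat definition point the other way, and neither covers this route. It is not a flat contradiction for investigator withdrawal, because Section 8 does not mention it.

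The actual size and direction are unknown, since no withdrawal rate is given. Under the assumptions above, the shift favours estrogen by about 0.2 to 0.4 points if a quarter of non-adherent estrogen-arm women are withdrawn at 6 months, and by about 0.7 to 2.2 points if all are. The calculation does not show a material false-positive risk. The point is worth acting on because the loss is avoidable and cheap to prevent, not because it is shown to be large.

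**What to change.** Reconcile 6.2.4 with Section 8 by stating that:

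- non-adherence to the cream does not by itself end outcome follow-up;
- such women keep their scheduled assessments through 12 months, with their permission, and are analysed as randomised;
- Section 8's continued evaluations and end-of-study evaluation also apply to withdrawal by the investigator, and include the primary-outcome components (POP-Q, bulge question, PGI-I and retreatment).

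One sentence in 9.5 should say how a woman without a 12-month outcome enters the primary comparison. Reporting withdrawal reasons by arm is optional; Form 20 already records them.

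The cost is a few sentences, plus the small effort of retaining women for visits already on the schedule. Nothing here changes when the cream is stopped.
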